4.7.2.2. Primary Analysis

The primary efficacy endpoint will be analyzed using a Mixed Model for Repeated Measures (MMRM) using the covariates described in Section 4.7.1 as fixed effects. The

model will also include week of treatment (as a categorical factor) and a treatment-by-visit interaction term, an interaction term between baseline MDS-UPDRS by visit will also be included. Within each participant, the model will incorporate an unstructured variance-covariance matrix for the random error terms. If the unstructured covariance matrix is non-estimable other covariance structures like heterogeneous autoregressive or compound symmetry would be used. Parameters will be estimated with the use of restricted maximum likelihood, and the Kenward-Roger method will be used for calculating the denominator degrees of freedom. Observations from different participants are considered independent. This model will be used to test the null hypothesis of no treatment difference at a two-sided α -level of 20% for the following comparisons:

- High dose vs placebo,
- Low dose vs placebo.

All the assessments that started after the “first symptomatic PD treatment date” (as defined in Section 4.3.1) will not be included in the analysis.

Missing scores (due to the assessments performed after the starting of symptomatic PD treatment or any other reason) for each of the individual parts of the MDS-UPDRS will not be imputed; they will be handled via the MMRM model. The MMRM assumes that missing data are missing at random (MAR). That is, MMRM assumes that given the statistical model and given the observed values of the endpoint, missing data are independent of the unobserved values (O’Kelly and Ratitch 2014). Correlation between successive observations on a subject allows data from subjects who dropped out to make a contribution to estimation of the effects at the final time point. The primary endpoint will also be summarized using descriptive statistics.

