4.7.5. Subgroup Analyses

A subgroup analysis will be performed if there are at least 20% of patients from the mITT population in the subgroup at baseline. The model used for the main analysis of the endpoint will be run in each subgroup; the model will exclude the subgroup being analyzed if that was a covariate (e.g. MAO-B Inhibitors at baseline (yes vs. no)). The estimated treatment effects (prasinezumab vs. placebo) and corresponding 80% CIs from the models will be displayed graphically in a forest plot for each prasinezumab dose level and each level of the subgroups specified.

The following subgroup analyses will be undertaken for the primary endpoint, change from baseline in total MDS-UPDRS (sum of Parts I, II and III) at Week 52. The subgroup analyses will also be undertaken in the following endpoints: MDS-UPDRS Part II, MDS-

UPDRS Part III, Part III subscores, and MDS-UPDRS sums of Part II and III, DaT-SPECT, digital PASADENA motor score, MoCA score and the composite time to event:

- MAO-B Inhibitors at baseline (yes vs. no)
- Hoehn & Yahr stage at baseline (1 vs. 2)
- REM Sleep Behavior Disorder Screening Questionnaire (RBDSQ) at baseline (RBDSQ ≥ 5 vs. < 5)
- Data-Driven sub-phenotypes (Diffuse malignant vs. mild motor-predominant vs. intermediate) at baseline
- Alpha-Synuclein Skin (positive vs. negative) (staining by immunohistochemistry on skin biopsy sections at baseline)
- DaT-SPECT ipsilateral putamen very abnormal vs. abnormal (defined on the baseline data with a validated cutoff of 0.6)

For the derivations of the data-driven sub-phenotypes, scales are classified into motor and non-motor. The motor scales are UPDRS-Part II (Motor symptoms) and UPDRS-Part III (Motor signs). The non-motor scales are SCOPA-AUT, RBDSQ and MOCA. After each one of the scales have been divided into percentiles, the data-driven sub-phenotypes are defined as follows:

- *Diffuse malignant* - Either motor score greater than the 75th percentile AND at least 1 non-motor score greater than the 75th percentile OR all 3 non-motor scores greater than the 75th percentile
- *Mild motor-predominant* - Motor and all non-motor scores less than the 75th percentile
- *Intermediate* - All those individuals not meeting criteria for other subtypes

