Symbol Digit Modalities Functional Test	Total Score
Passive Monitoring – Turning	Median Turn Speed
Passive Monitoring – Gestures	Median Turn Speed

Each feature will be first normalised. Feature values will be aggregated by average over reported window (Table 5). Feature values will be considered missing if less than 3 feature values exist in this interval. The same random coefficients model used for primary analysis will be used for analysis of the dBm features. Assessment taken after the start of symptomatic PD treatment (described in Section 4.3.1) will not be included in the analysis.

Absolute change in digital PASADENA motor score – Remote Monitoring

The digital PASADENA motor score will be mapped according to the time windows described in Table 5. An average of the dBm score will be calculated for each visit using all the scores that are mapped within a single reporting window. Assessment taken after the start of symptomatic PD treatment (as described in Sections 4.3.1) will not be included in the analysis. A random coefficients model will be used for the analysis of the

dBM. The model involves a random intercept and a slope for each subject. Within each participant, the model will incorporate an unstructured variance-covariance matrix for the random error terms. If the unstructured covariance matrix is non-estimable other covariance structures like heterogeneous compound symmetry would be used. Parameters will be estimated with the use of restricted maximum likelihood, and the Kenward-Roger method will be used for calculating the denominator degrees of freedom.

Percent change in digital PASADENA motor score - Remote Monitoring

Percent change in digital PASADENA motor score will be analyzed in the same way as the absolute change in digital PASADENA motor as described above

Digital PASADENA motor Score – In Clinic Assessments

The digital PASADENA motor score derived from in clinic assessments will be analysed as the one obtained from remote monitoring, the only difference will be that the average of the dBM score will be over the time windows described in Table 4

Digital Biomarker Single Features – In Clinic Assessments

Selected features from the digital biomarker in clinic assessments will be analysed in the same way as the features from the remote monitoring.

dBM ePROs: PAC-SYM, Hospital Anxiety and Depression Scale (HADS), EQ-5D-5L will be analysed via ANCOVA and/or random coefficients model.

Diary Questions

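### The exploratory digital motor score model puts a random intercept and slope on top of an unstructured residual covariance, which leaves the random effects redundant, and the single-feature analysis points to the wrong model

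*SAP*

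**What the plan says.** SAP Appendix 1, in the paragraph on absolute change in the digital PASADENA motor score from remote monitoring, specifies a random coefficients model: "The model involves a random intercept and a slope for each subject. Within each participant, the model will incorporate an unstructured variance-covariance matrix". The sentence goes on to assign the matrix to the random errors, not to the random effects. If that fails, "If the unstructured covariance matrix is non-estimable other covariance structures like heterogeneous compound symmetry would be used". Estimation is by REML with Kenward-Roger degrees of freedom. The paragraph maps scores to the Table 5 windows but does not name the time variable behind the slope.

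Other analyses take over this text. Percent change is handled in the same way. For the in-clinic score, "the only difference will be that the average of the dBM score will be over the time windows described in Table 4". The paragraph on single features from remote monitoring says "The same random coefficients model used for primary analysis will be used for analysis of the" individual features.

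SAP section 4.7.2.2 describes a different kind of model for the primary endpoint: "The primary efficacy endpoint will be analyzed using a Mixed Model for Repeated Measures (MMRM"), with week as a categorical factor and no random intercept or slope. Its covariance sentence is "Within each participant, the model will incorporate an unstructured variance-covariance matrix for the random error terms", which matches the Appendix 1 sentence word for word.

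The score is also used outside the appendix. The endpoint list in SAP section 4.7.5 includes "digital PASADENA motor score, MoCA score and the composite time to event", and each endpoint's main model is to be run within subgroups under this rule: "A subgroup analysis will be performed if there are at least 20% of patients from the mITT population in the subgroup at baseline". Protocol section 6.8 lists a random coefficients model for the digital endpoints and gives no covariance detail.

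**The concern.** Random effects and a residual covariance matrix are two ways of describing the same within-patient dependence. A random coefficients model gets its covariance from the intercept and slope plus a simple residual. An MMRM gets it from the unstructured matrix alone. Appendix 1 asks for both at once, so the part that makes the model a random coefficients model has nothing left to explain.

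Three things follow. The first-choice model has variance components that cannot be separated, so non-convergence or arbitrary estimates of them are likely. The analyst is then sent to a fallback that is only an example, and has to settle the structure after seeing the data. And a programmer who follows the single-feature paragraph literally finds an MMRM where a random coefficients model was promised.

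The stakes are limited. These analyses are exploratory, and Appendix 1 says that they might not appear in the CSR. The main-body subgroup use in section 4.7.5 is the one place where the model reaches beyond the appendix.

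**Working it through.** The documents give no sample size, power or precision figure for the digital score, so there is no stated figure to reproduce. The check has two parts.

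**1. Identifiability.** The marginal covariance is V = ZGZ' + R. Z holds a column of ones and the times, G is the 2x2 covariance of the random intercept and slope (3 parameters if they may correlate; the SAP does not give its structure), and R is the residual matrix. An unstructured R for k windows has k(k+1)/2 parameters.

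- SAP Table 5 has 26 post-baseline windows: 26 x 27 / 2 = 351, plus 3 = 354 parameters.
- SAP Table 4 has 7 post-baseline windows: 7 x 8 / 2 = 28, plus 3 = 31 parameters.

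The rank of the Jacobian of V with respect to all parameters, on nominal window times, is:

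| Residual structure, with G kept | Table 5: rank of parameters | Table 4: rank of parameters |
|---|---|---|
| Unstructured (as written) | 351 of 354 | 28 of 31 |
| Heterogeneous compound symmetry, general SDs | 30 of 30 | 11 of 11 |
| Same, SDs constant or linear in time | 29 of 30 | 10 of 11 |
| Homogeneous compound symmetry | 4 of 5 | 4 of 5 |
| Independent, constant variance | 4 of 4 | 4 of 4 |
| AR(1) | 5 of 5 | 5 of 5 |
| Independent, window-specific variances | 29 of 29 | 10 of 10 |

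In the first row the rank equals that of the unstructured matrix alone, so the three parameters of G add nothing.

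If patient-specific times are used instead (assumed here to vary by up to 4 days around nominal), the ranks become 353 of 354 and 30 of 31. The intercept variance adds the same constant to every element of V whatever the times, so R always absorbs it. The slope terms are then identified only through the small timing differences.

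If G was the matrix meant to be unstructured, the named fallback changes nothing: for a 2x2 matrix, heterogeneous compound symmetry also has two variances and one correlation, 3 parameters.

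**2. Precision cost of keeping the unstructured matrix.** Assumptions: a mean linear in time in each of three equal arms, complete data, and a true random intercept and slope with independent errors. The variance of the treatment contrast is inflated by (df - 1) / (df - 1 - (p - 2)), with df = n - 3 and p windows. The total n = 316 is the safety-evaluable number in Protocol section 1.3.2. A subgroup at the 20% threshold has 0.20 x 316 = 63 patients. One at the 15% threshold that Appendix 1 sets for GBA has 0.15 x 316 = 47.

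| n | Table 5 (p = 26) | Table 4 (p = 7) |
|---|---|---|
| 316 | 312/288 = 1.08 | 312/307 = 1.02 |
| 63 | 59/35 = 1.69 | 59/54 = 1.09 |
| 47 | 43/19 = 2.26 | 43/38 = 1.13 |

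Simulation with intercept, slope and residual variances all set to 1 (assumed) gave 1.07, 1.71 and 2.26 on Table 5 and 1.02, 1.09 and 1.13 on Table 4 for the slope difference. The Week 52 difference gave nearly the same. With monotone dropout at the non-evaluable rates of SAP Table 1, the n = 316 factors were 1.115 (Monte Carlo error about 0.02) and 1.025. Subgroup runs on Table 5 with dropout were unstable, so no figure is given for them.

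**The case against.** The strongest reply is that the plan provides for the problem. It moves to another structure if the unstructured matrix cannot be estimated, and its example is identified in general even with the random effects kept. A reader might infer that the model cannot be fitted at all. The documents do not support that: the marginal covariance and the treatment contrast are estimable, software may return them with a warning, and a workable fallback is named. What remains is that the fallback is one example without an order, and that it does not settle whether the random effects stay. The primary MMRM also leaves its fallback open, but its first choice is identified.

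Second, full redundancy needs nominal times, which Appendix 1 does not specify. This stands, and it narrows the defect to the intercept variance if actual times are used.

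Third, the factors 1.69 and 2.26 are tempting as headline figures. They need the remote score (neither subgroup passage says which version is meant), a subgroup exactly at its threshold, complete data although assessments after symptomatic treatment are dropped, and a 26x26 matrix that survives fitting. That is where the fallback would most plausibly take over. The figures also measure the cost of the unstructured matrix, not of the redundancy.

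Fourth, the cross-reference is editorial. The digital-score model is almost certainly meant, because it is the only random coefficients model specified. This stands as to intent, but the reference is false as written. A reader should not infer that a random coefficients model was planned for the primary endpoint.

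Fifth, the Health Survey paragraph also names a random coefficients model, but nothing ties it to this covariance text, so the defect should not be extended to it.

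Finally, Appendix 1 mentions a separate document on how the digital score's model is constructed. It probably concerns deriving the score, but it is not available here.

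**Conclusion.** The specification is wrong as written, and the point is minor. On nominal window times the random intercept and slope are wholly redundant beside an unstructured residual matrix. On actual times the intercept variance is still unidentified. Treatment contrasts stay estimable, and nothing here implies bias.

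At full sample the cost of keeping the unstructured matrix is about 8% in variance on the remote grid and 2% on the in-clinic grid, given a true random intercept and slope, a linear mean and complete data. It grows in small subgroups on the remote grid, but there the matrix may not be retained, so the larger factors are a conditional worst case. The primary analysis is untouched. The practical harm is an avoidable analyst choice on an exploratory endpoint that also feeds main-body subgroup analyses, and a cross-reference that leads to the wrong model.

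**What to change.** In SAP Appendix 1, replace the covariance text for the digital score with a statement that:

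- the unstructured matrix is the 2x2 covariance of the random intercept and slope;
- the slope uses a named time variable (nominal window time or actual assessment time);
- the residuals follow one simple structure fixed in advance. Independent errors with constant variance are one reasonable choice. AR(1) or window-specific variances are equally acceptable and also identified. The Table 5 windows differ in length, which is an argument for window-specific variances. If residuals are truly AR(1) with correlation 0.5 (assumed), treating them as independent costs about 3% to 4% in slope variance;
- if the fit fails to converge or the 2x2 matrix is not positive definite, the intercept-slope covariance is set to zero, and if the slope variance is still estimated at zero, a random intercept alone is used;
- REML and Kenward-Roger are kept.

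The same paragraph should name the fixed time terms and the treatment contrast, which it does not state. The treatment covariate itself is already supplied by SAP section 4.7.1. In the single-feature paragraph, refer to the model used for the digital PASADENA motor score instead of the primary analysis.

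The cost is a few sentences, with no effect on data collection.

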###### **4.2.2 Inclusion Criteria**

Participants must meet the following criteria for study entry:

1. Idiopathic PD with bradykinesia plus one of the other cardinal signs of PD (resting tremor, rigidity) being present, without any other known or suspected cause of PD untreated or treated with MAO-B inhibitor.
2. Male or female, 40 to 80 years of age, body weight range of  $\geq 45$  kg/99 lbs to  $\leq 110$  kg/242 lbs and a body mass index (BMI) of 18 to 34 kg/m^2.
3. A diagnosis of PD for 2 years or less at screening.
4. H&Y Stage I or II.

5. A screening brain DaT-SPECT consistent with PD (central reading).
6. Clinical status does not require dopaminergic PD medication and is not expected to require dopaminergic treatment within 52 weeks from baseline.
7. If presently being treated for PD, a stable dose of MAO-B inhibitor (rasagiline or selegiline) for at least 90 days prior to baseline and not expected to change within 52 weeks.
8. Able and willing to provide written informed consent and to comply with the study protocol according to ICH and local regulations.
9. For women of childbearing potential: use of highly effective contraceptive methods (that result in a failure rate of < 1% per year) during the treatment period and for at least 30 days (or longer if required by local regulations) after the last dose of study drug.

A woman is considered to be of childbearing potential if she is post-menarcheal, has not reached a post-menopausal state ( $\geq 12$  continuous months of amenorrhea with no identified cause other than menopause), and has not undergone surgical sterilization (removal of ovaries and/or uterus).

Examples of highly effective contraceptive methods (with a failure rate of < 1% per year) include bilateral tubal ligation, vasectomized partner, established, proper use of hormonal contraceptives that inhibit ovulation, hormone-releasing intrauterine devices, and copper intrauterine devices.

The reliability of sexual abstinence should be evaluated in relation to the duration of the clinical trial and the preferred and usual lifestyle of the patient. Periodic abstinence (e.g., calendar, ovulation, symptothermal, or postovulation methods) and withdrawal are not acceptable methods of contraception.

10. For men: use of contraceptive measures as defined below:

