The diary contained four questions related to symptoms with categorical responses ranging from 1 (no symptoms) to 6 (severe symptoms), three questions related to difficulty with sleeping with four categorical responses 1 (not at all) to 4 (a lot), two questions related to bowel movement with binary responses (Yes or No), and one question related to the number of nights with problems with sleep with categorical responses (Never, 1 night, 2-3 nights, 4-5 nights, 6-7 nights). The diary also contained a Health Survey with 5 questions capturing the number of days the patient had health related problems.

Each one of the responses from the diary questions will be mapped according to the windows described in Table 5. For questions with more than two categories, categorical responses will be treated as continuous and an average during the reporting window will be used for analysis; a random intercept model will be used for the analysis. For the questions with binary responses a logistic regression will be applied. Responses from the Health Survey will be analysed with a random coefficients model.

Exploratory subgroup analyses

The following subgroup analyses are exploratory and might not be reported in the clinical study report.

The following subgroup analyses will be undertaken for the primary endpoint, change from baseline in total MDS-UPDRS (sum of Parts I, II and III) at Week 52. The subgroup analyses will also be undertaken in the following endpoints: MDS-UPDRS Part II, MDS-UPDRS Part III, and MDS-UPDRS sums of Part II and III, DaT-SPECT, dBM score, MoCA score and the composite time to event. The subgroup analyses will be undertaken in the same way described for the subgroups analyses in Section 4.7.5:

- Age at baseline (< 60 years vs. ≥ 60)
- Gender (male vs. female)
- Disease duration (<12 months vs. >12 months)
- Age at diagnosis of Parkinson's disease (< 60 years vs. ≥ 60)
- Nucleus basalis of Meynert at baseline (atrophy vs. no atrophy)
- MoCA total score: lower (<22) vs. higher (>22)
- GBA Mutation (positive vs negative). This subgroup analysis will only be done if there are 15% of patients from the overall population.
- Motor sub-phenotypes:
 - tremor vs. akinetic-rigid vs. intermediate
 - tremor vs. postural instability gait dysfunction vs. indeterminate

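### Two exploratory subgroup splits (MoCA at 22, disease duration at 12 months) leave the boundary value in neither level, so boundary patients enter neither fitted model for that split

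*SAP*

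**What the plan says.** The exploratory subgroup list at the end of SAP Appendix 1 includes "MoCA total score: lower (<22) vs. higher (>22") and "Disease duration (<12 months vs. >12 months"). Both cuts use < on one side and > on the other.

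Two other numeric cuts in the same list are written differently: "Age at baseline (< 60 years vs. ≥ 60") and "Age at diagnosis of Parkinson's disease (< 60 years vs. ≥ 60").

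For method, the Appendix refers back to the main body: "The subgroup analyses will be undertaken in the same way described for the subgroups analyses in Section 4.7.5". SAP Section 4.7.5 then gives two rules that matter here. On fitting: "The model used for the main analysis of the endpoint will be run in each subgroup". On size: "A subgroup analysis will be performed if there are at least 20% of patients from the mITT population in the subgroup at baseline".

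The Appendix applies its subgroups to the primary endpoint and to seven others: MDS-UPDRS Part II, Part III, Parts II and III summed, DaT-SPECT, the digital score, MoCA, and the composite time to event. It also says that these analyses are exploratory and may be left out of the CSR.

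**The concern.** A two-level subgroup should place every patient with a known value in exactly one level. These two definitions do not, and no other section of the SAP or protocol assigns the boundary values. The subgroup list in Protocol Section 6.6 does not contain either split.

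Because each level is fitted on its own, an unassigned patient is in neither model for that split, whichever of the eight endpoints is analysed. The two forest-plot rows then do not add up to the patients with a known value. The gap also touches the size rule: patients at the boundary count toward neither level, which could decide whether a level near 20% is analysed at all.

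**Working it through.** No figure in the plan needs reproducing, since no sample size, power or error rate is involved. The check is whether each definition covers every attainable value.

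**Inputs**
- MoCA cut: <22 vs >22 (SAP Appendix 1). Whole scores from 0 to 30 are assumed; the documents do not give the range.
- Duration cut: <12 vs >12 months (SAP Appendix 1). Protocol Section 4.2.2 requires "A diagnosis of PD for 2 years or less at screening", so 12 months lies inside the enrolled range of roughly 0 to 24 months.
- Control: age <60 vs ≥60 (SAP Appendix 1), ages 40 to 80 (Protocol Section 4.2.2).
- Patient count: 316 safety-evaluable participants (Protocol Section 1.3.2), used as a stand-in for the mITT population.

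**Step 1: values in neither level**

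| Split | Values checked | In neither level as written | In neither level with one side inclusive |
|---|---|---|---|
| MoCA | 0 to 30, whole scores | 22 | none |
| Disease duration | 0 to 24, whole months | 12 | none |
| Age (control) | 40 to 80, whole years | none | not applicable |

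**Step 2: is this lost typography or a house convention?** Neither is likely. The ≥ sign is intact in the age bullets of the same list and in the RBDSQ cut of SAP Section 4.7.5 (≥5 vs <5). The data-driven sub-phenotypes in that section also use strict inequalities around a percentile, but they add an intermediate level that takes everyone else. The MoCA and duration splits have no such level.

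**Step 3: how many patients?** The documents give no distribution for either variable, so only conditional figures are possible.
- Duration computed from exact dates: almost nobody is at exactly 12 months, so about 0%.
- Duration in whole months, spread evenly over 0 to 24: 1/25 = 4%, and 0.04 × 316 = 12.6, about 13 patients. Both conditions are assumptions. The SAP states neither the unit nor the rounding, and uneven recording would change the figure.
- MoCA: the share scoring exactly 22 is unknown. For illustration only, assumed shares of 1% and 8% give 0.01 × 316 = 3.2 and 0.08 × 316 = 25.3, that is about 3 to 25 patients.

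**Step 4: size rule.** 0.20 × 316 = 63.2, so a level needs 64 patients. The GBA bullet in the same list sets its own 15% threshold, which fits with the 20% rule applying to the others. Patients at a boundary value are not counted in either level.

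**The case against.** The case for leaving this alone is that very little depends on it. SAP Section 1 puts the analyses for the CSR and for Phase 3 decisions in the main body and only exploratory ones in Appendix 1, and the Appendix says these subgroups may go unreported. The RBDSQ cut in Section 4.7.5 has no gap. The duration gap may be almost empty if dates are used. The MoCA split may never run: entry excludes an MMSE of 25 or below (Protocol Section 4.2.3), so fewer than 20% of patients may score below 22, although the documents give no MoCA distribution to settle this. All of that stands, and it places the point at the lowest severity. It does not make the definitions correct.

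Three stronger readings are tempting and are not supported.
- A reader might infer that the boundary is open to assignment after results are seen. Taken literally, the text excludes these patients and leaves nothing to assign. Literal exclusion and later assignment cannot both be claimed as harms, and the documents show no intention to reassign.
- A reader might infer that patients are lost from the efficacy analyses generally. They are missing only from the split whose boundary they sit on; they remain in every main analysis and are not removed from any other subgroup analysis.
- A reader might infer that ≥ was plainly intended. The age cuts suggest it, but ≤22 vs >22 and ≤12 vs >12 months would close the gaps equally well, and nothing in the documents says which side was meant.

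**Conclusion.** The two definitions are wrong as written, and the consequence is minor. Followed literally, they omit patients with a MoCA of 22 from both MoCA-split models, and patients at exactly 12 months from both duration-split models, and leave them out of the size count. This conclusion rests on the text alone, plus the assumption that MoCA totals are whole numbers, so that 22 can occur. The number affected is not derivable: for duration, about 0% with exact dates and about 4% under even whole-month recording; for MoCA, unknown. The primary analysis, the main-body subgroup analyses, the sample size and the error rate are unaffected.

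**What to change.** Before the analysis, make one side of each cut inclusive. Writing <22 vs ≥22 and <12 vs ≥12 months would match the age cuts in the same list; the sponsor should confirm that this is the intended side. For duration, it would also help to state whether it is computed from dates or recorded in months, and how it is rounded, because that determines who sits at the cut. The cost is a short edit to two bullets. It needs no new data and changes no other analysis.
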